1.2 STUDY RATIONALE & JUSTIFICATION

We wish to formally assess, in a randomized controlled study, whether a modified approach using boiled peanut for peanut OIT can result in desensitisation and sustained unresponsiveness (i.e. tolerance) to roasted peanut. We will assess the safety of this approach, and study the immunological mechanisms involved, our secondary aim being to develop clinically-useful predictors for identifying individuals likely to undergo successful desensitization.

STUDY HYPOTHESIS:

A pragmatic protocol utilizing increasing doses of boiled peanut can induce desensitisation to roasted peanut, in peanut-allergic individuals, with an acceptable safety profile.

¹Turner PJ, Gowland MH, Sharma V, et al. Increase in anaphylaxis-related hospitalizations but no increase in fatalities: An analysis of United Kingdom national anaphylaxis data, 1992-2012. JACI 2014; doi: 10.1016/j.jaci.2014.10.021.

²Bégin P, Paradis L, Paradis J, Picard M, Des Roches A. Natural resolution of peanut allergy: a 12-year longitudinal follow-up study. JACI In Practice 2013;1:528-30.e1-4.

³Wood RA, Sampson HA. Oral immunotherapy for the treatment of peanut allergy: is it ready for prime time? IACI In Practice 2014;2:97-8.

⁴Vickery BP, Scurlock AM, Kulis M, et al. Sustained unresponsiveness to peanut in subjects who have completed peanut oral immunotherapy. JACI 2014;133:468-75.

⁵Tang ML, Ponsonby AL, Orsini F, et al. Administration of a probiotic with peanut oral immunotherapy: A randomized trial. J Allergy Clin Immunol. 2015. doi: 10.1016/j.jaci.2014.11.034.

⁶Turner PJ, Mehr S, Sayers R, et al. Loss of allergenic proteins during boiling explains tolerance to boiled peanut in peanut allergy. JACI 2014;134:751-3.

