As with most OIT studies, this study will be **open label**, as we wish to assess a pragmatic approach to dosing which would not be possible with blinding. Families will be provided with a specific peanut cultivar (Holt Runner, Peanut Company of Australia Ltd); families will be given specific instructions on preparing the peanut for OIT (through boiling) at home. The supply of raw peanuts direct from the wholesaler also reduces potential nut-contamination. We have chosen a specific cultivar with higher oleic oil content, resulting in a longer shelf-life (at least 18 months when vacuum packed and stored at 4°C). To perform OIT safely, supervision and frequent appointments to the research unit are required. A blinded study would increase the burden on families. Finally, the use of blinding might lead participants (and their families) to believe they are indeed tolerant to peanut and therefore result in less stringent allergen avoidance, putting them at increased risk of accidental reactions.

We have chosen a daily maintenance dose of 800mg roasted peanut protein, on the basis of previous reports that this amount is generally well-tolerated by subjects undergoing OIT on an daily basis, and is also associated with a suggestion of efficacy. Our primary endpoint (able to tolerate 1.4mg roasted peanut protein, equivalent to \geq 6 roasted peanuts) has been chosen on the basis of efficacy and ability to protect against accidental exposure to peanut in the community. This will be assessed using a blinded food challenge, an established research tool in food allergy.

The inclusion of an assessment to determine tolerance (sustained unresponsiveness) to peanut in the absence of ongoing daily peanut exposure is essential. The realities of day-to-day life mean that outside the safety of a clinical trial, maintenance peanut doses are often omitted. It is therefore important to demonstrate ongoing tolerance to peanut in the absence of daily maintenance. Furthermore, the reassurance through the demonstrated tolerance in children with previous peanut allergy may well improve quality of life further. This outcome needs to be corrected for the possibility of natural resolution, thus a comparison to controls who have not undergone OIT is required.

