5.8.2 QUALITY OF LIFE ASSESSMENTS

The impact of OIT on participants' quality of life (QoL) will be assessed both from parents' and participants' perspective using abbreviated versions of disease-specific validated "food-allergy quality of life questionnaire" (FAQL-Q) in its parental, ¹⁴ child¹⁵ and teenage¹⁶ forms at baseline, 3, 6, 12, 24 and 36 months in both the active and control groups. These new abbreviated versions have been validated (data submitted for publication). We will also assess the impact of the child's food allergy on parent QoL, using the FAQL-Parent Burden form (which has been validated in a UK population).¹⁷ QoL assessments will be done both prior to and after oral challenges.

The FAQL-questionnaires are based on a 7-point Likert scale and changes greater than 0.5 points over time have been defined as clinically significant. Previous studies have reported a positive effect on QoL following OIT to peanut from the parents' perspective, however, there are no controlled studies which have addressed the impact on QoL as perceived by participants. This is a significant knowledge gap, since there is a concern that while parents report an improved QoL when their child undergoes OIT, the child themselves may experience a worsening of QoL due to frequent side effects and need to alter their activities following OIT doses.

In line with current expert opinion, and to ensure the ability to compare responses consistently during the first 12 months of OIT, children who are age 12 at study commencement will be asked to complete the Teenage versions of the QoL assessments, unless there are difficulties with comprehension which preclude this.

We will also assess parental anxiety before, and 12 and 24 months after their child commencing OIT, using the Perceived Stress Scale.¹⁹

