It is therefore important for this study to include mechanistic assessments to allow for markers of successful desensitisation to be assessed, in order to improve the efficacy of future OIT protocols. We will include a series of laboratory assessments in subjects undergoing OIT, allowing longitudinal comparisons to be made in those undergoing OIT (vs controls) to assess the following:

- Changes in serum specific antibodies pre- and post-OIT: Total IgE; specific IgE, IgG4 to whole peanut and peanut components (Ara h 1, 2, 3, 8 and 9) and their ability to cause an effector cell response will be measured
- IgE-immunoblot using patient sera to identify in vitro the binding of participants IgE to peanut proteins, and how this varies during OIT.
- Identification of serum factors associated with the development of oral tolerance during peanut OIT, by means of a validated IgE facilitated-binding assay.
- Changes in basophil responses (assessed by CD63 and CD203c expression by flow cytometry) following *in vivo* and *ex vivo* peanut stimulation, and how these vary during OIT. Confirmatory work will be performed in a subset of patients using purified basophils isolated from whole blood.
- Biomarkers that may identify successful tolerance induction to peanut
- Changes in T and B cell populations and their immune profile during OIT, including allergen-specific proliferation of T-cell subtypes (including T helper and regulatory T cells) and changes in immunoglobulin repertoire by peanut-specific B-cells.
- mRNA expression and methylation of proteins (such as forkhead box protein 3 (FOXP3) sites) on T cell subsets which may predict the presence of sustained unresponsiveness.

These assessments will be performed on blood samples taken at baseline, 3, 6, 12, 13 and 24 months, as well as at the 3 year assessments (outlined in Figure 8) after commencement of OIT. Laboratory work will be initially performed at the National Heart & Lung Institute, Imperial College London, although some assays may be performed elsewhere in the UK or abroad, where lack of local expertise necessitates this). Specimens may also be stored for future use in new assays to measure immune responses or biomarkers, as research tests are developed.

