7.2.2 ANALYSIS OF SECONDARY ENDPOINTS

The following secondary analyses will be performed, using two-sided testing for non-parametric data at a p<0.05 level of significance:

- Relative change in clinical threshold (NOAEL, LOAEL) to roasted peanut at 6 and 12 months in active vs control, using Mann-Whitney U test.
- Proportion of subjects who tolerate 1.4g (or more) roasted peanut protein in the active and control groups, 12 months after randomization and following cessation of all peanut intake for 4 weeks after 1 and 3 years of OIT, using a two-sided Fisher's exact test at a p<0.05 level of significance.
- Change in quality of life assessments before, and at 6 and 12 months after OIT, as assessed by FAQL-Questionnaire in children, teenagers and their parents in the active vs control groups using paired and group comparisons by non-parametric testing.
- The incidence of adverse events experienced between active and control groups. Statistical differences will be
 determined using Fisher's exact test for proportions or using non-parametric tests for graded reactions.
 Logistic regression will be used to assess the influence of age, gender, asthma status and prior history of
 anaphylaxis on incidence of adverse events.
- Immunological outcome measures pre-, during and post- 12 months of OIT, using Mann-Whitney U test (for paired comparisons) or Friedman's test (for trends over time).

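### Section 7.2.2 applies an unadjusted p<0.05 significance rule to every secondary analysis, with no hierarchy, correction or exploratory label; for the 9 to 14 between-arm tests that can be counted, the chance of at least one false positive is about 27% to 51% (assumed correlation 0.5 down to independence)

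*Combined protocol and SAP*

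**What the plan says.** Section 7.2.1 defines one primary test: tolerance of 1.4 g at 12 months, active against control, by two-sided Fisher's exact test at 0.05. Section 7.2.3 plans no formal interim analysis.

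Section 7.2.2 then sets one rule for all secondary endpoints: "The following secondary analyses will be performed, using two-sided testing for non-parametric data at a p<0.05 level of significance". Five groups of analyses follow:

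- Threshold: "Relative change in clinical threshold (NOAEL, LOAEL) to roasted peanut at 6 and 12 months in active vs control, using Mann-Whitney U test".
- Sustained unresponsiveness: the 1.4 g proportion "following cessation of all peanut intake for 4 weeks after 1 and 3 years of OIT", by Fisher's exact test.
- Quality of life: FAQL-Q in children, teenagers and parents at 6 and 12 months, with both paired and between-group tests.
- Adverse events: Fisher for proportions or non-parametric tests for grades, plus a logistic regression on four covariates.
- Immunology: tests before, during and after 12 months of treatment, number not stated.

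Other sections widen the choice of data. On quality of life, section 5.8.2 says "QoL assessments will be done both prior to and after oral challenges", and 7.2.2 does not say which score is tested. Section 5.8.3 lists the antibodies as "Total IgE; specific IgE, IgG4 to whole peanut and peanut components (Ara h 1, 2, 3, 8 and 9", alongside basophil, T-cell, B-cell and mRNA measures. Section 7.2 adds a per-protocol analysis.

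**The concern.** A p<0.05 level of significance is a decision rule, and 7.2.2 words it as it is worded for the primary. As written, one questionnaire form at one visit, or one antibody, would qualify as a significant secondary effect however many others were tested.

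The setting makes that matter. The trial has 46 children, 16 of them controls. It is open label, and quality of life is reported by the children and their parents. Some secondary questions also carry weight in the protocol. Section 1.2 describes "our secondary aim being to develop clinically-useful predictors for identifying individuals likely to undergo successful desensitization", and section 3.2 says "The inclusion of an assessment to determine tolerance (sustained unresponsiveness) to peanut in the absence of ongoing daily peanut exposure is essential". A reader of the results could not tell which secondary findings were meant to bear weight and which were screening.

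**Working it through.** **The plan's own figure.** The protocol gives no family-wise error rate for the secondary endpoints. Its only checkable figure at this alpha is the primary sample size. For 10% v 60%, 2:1, two-sided 0.05, 80% power and continuity correction, the two-proportion formula gives 12.75 + 25.5 = 38.25. Multiplying by 1.2 for dropout gives 45.9, that is 46, as stated in 7.1 (dividing by 0.8 gives 47.8). The stated 0.05 is therefore the full level of the one primary test.

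**Counting the between-arm secondary tests.**

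| Group (7.2.2) | Fullest reading | Clearly described concurrent control | Reason for the difference |
|---|---|---|---|
| Threshold | 2 measures x 2 times = 4 | 2 (12 months) | 5.3.4.2 describes the 6-month roasted challenge only as an active-arm step |
| Sustained unresponsiveness | 2 (1 and 3 years) | 0 | 5.4.2 limits the 13-month challenge to active-group responders (5.4 is looser); controls are offered OIT from month 12 |
| FAQL-Q | 3 respondent groups x 2 times = 6 | 6 | 5.3.3 assesses controls at 6 and 12 months |
| Adverse events | 2 (incidence and grade) | 1 | the two tests are joined by or |
| Total | 14 | 9 | |

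Both totals leave out the paired quality-of-life tests, the logistic covariates, the Parent Burden form, the per-protocol repeats and the immunology panel.

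**Formulas.** For k independent tests at level 0.05, P(at least one p<0.05) = 1 − 0.95^k:

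- k = 9: 1 − 0.95^9 = 0.370
- k = 14: 1 − 0.95^14 = 0.512

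For test statistics with a common correlation ρ, let c = 1.96 and Z be standard normal. The probability is then 1 − E{[Φ((c − √ρ Z)/√(1−ρ)) − Φ((−c − √ρ Z)/√(1−ρ))]^k}, by numerical integration:

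| k | ρ = 0 | 0.3 | 0.5 | 0.7 | 0.8 | 0.9 |
|---|---|---|---|---|---|---|
| 9 | 37.0% | 32.6% | 26.9% | 20.2% | 16.5% | 12.4% |
| 14 | 51.2% | 43.8% | 34.8% | 24.9% | 19.7% | 14.1% |

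The documents give no correlations. A single ρ is also a rough model, because the child and teenage forms are completed by different children. With ρ = 0.5 inside each endpoint group and 0 between groups, the results are 31.5% for 9 tests and 44.7% for 14.

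**Allowing for Fisher's conservatism.** With 24 to 30 active and 12 to 16 control children and common rates of 10%, 30% or 50%, the actual size of a nominal 0.05 Fisher test is about 1.5% to 3.8%. At most one of the 9 tests is a Fisher test. Taking its size as 1.5% gives 1 − 0.95^8 × 0.985 = 34.7% under independence. Up to three of the 14 are Fisher tests: 1 − 0.95^11 × 0.985^3 = 45.6%.

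**Immunology.** The antibody list alone is 1 total IgE + 2 antibody types x 6 targets = 13 measures. One test each would give 1 − 0.95^13 = 48.7% if independent and 33.4% at ρ = 0.5. This only illustrates scale, since the plan does not state how many tests will be run.

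**The case against.** The case for leaving 7.2.2 alone is reasonable. This is a single-centre phase 2 trial with one primary endpoint, one test and its own alpha. The other outcomes are labelled secondary, and many such trials report unadjusted secondary p-values. Section 5.8.3 is worded tentatively about what markers might show. The count can also be cut further. One arm eats peanut daily and the other avoids it, so a true null for adverse events is implausible; without that test, 8 remain (33.7% independent, 25.0% at ρ = 0.5). NOAEL and LOAEL come from the same dose ladder and are close to one test; merging them leaves 7 (30.2% independent).

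Much of this stands, and it limits what can be said. Several stronger readings are tempting, but the documents do not support them:

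- *That there are at least 14 between-arm tests.* Fourteen is the fullest reading of the bullets and not a floor.
- *That the error rate is 35% instead of a promised 5%.* The 35% needs 14 tests and an assumed correlation of 0.5, and the plan never says the secondary family is held at 5%.
- *That the immunology panel means 39 antibody tests (13 measures at 3, 6 and 12 months).* Section 7.2.2 offers Friedman's test for trends, which is one test per measure.
- *That the protocol has declared these endpoints confirmatory.* In section 3.2, essential refers to including the tolerance assessment. Section 1.2 states an aim and sets no rule for claims.
- *That the trial's main conclusion is at risk.* The primary test is untouched.

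The objection does not remove the rule itself. Calling an outcome secondary does not say how its p-value is to be read, and 7.2.2 says it is to be read against 0.05. Every count above still gives a family-wise rate well over 5%.

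**Conclusion.** The point holds as a gap in the reporting rules. Section 7.2.2 attaches an unadjusted two-sided 0.05 significance rule to every secondary analysis and provides no hierarchy, correction or exploratory label. If all nulls are true, the chance of at least one false positive is about 27% to 37% for the 9 tests with a clearly described concurrent control, and 35% to 51% for the fullest count of 14. Each range runs from a common correlation of 0.5 to independence. At a correlation of 0.8 the figures fall to about 17% and 20%.

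These figures rest on assumed correlations and on each test having its nominal size, so Fisher tests pull them down somewhat. The immunology panel would push the overall chance up by an amount the plan does not let one calculate. The remedy is a cheap improvement; the primary result does not depend on it.

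**What to change.** In 7.2.2, replace the blanket p<0.05 rule with a statement that:

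- secondary analyses are exploratory and will be reported as estimates with 95% confidence intervals and unadjusted nominal p-values, with no claims of significance;
- for the immunology panel, Benjamini-Hochberg adjusted p-values at a 5% false discovery rate will be reported, and any predictor found will be described as hypothesis-generating.

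If the sponsor wants a confirmatory secondary claim, add a short fixed sequence. It would be tested only after a significant primary result, each step at two-sided 0.05, stopping at the first non-significant step. It should start with an endpoint that has concurrent randomised control data: the 12-month threshold, using one named measure (NOAEL or LOAEL). Sustained unresponsiveness should enter only once the plan states how controls are classified, because section 3.2 requires a comparison with controls while 5.4.2 describes the 13-month challenge for the active group only. Quality of life should enter only once the plan states how the child and teenage forms are combined and whether the pre- or post-challenge score is used.

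The cost is a few sentences, with no new patients, visits or data. The downside is that isolated nominal p<0.05 secondary results could no longer be reported as significant. If a sequence is used, a failed early step blocks the later ones.

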5.2 DOUBLE-BLIND, PLACEBO-CONTROLLED FOOD CHALLENGE (DBPCFC) TO ROASTED PEANUT

All participants who fulfil eligibility criteria for the study will undergo a baseline DBPCFC to roasted peanut at enrolment. The DBPCFC is established as the gold-standard test of diagnosis of food allergy by international consensus. The objectives are:

- i. to confirm the diagnosis of IgE-mediated peanut allergy,
- ii. to determine the threshold of clinical reactivity to peanut prior to OIT

The DBPCFC involves 2 half-day visits, at least one week apart. Participants are given incremental doses of peanut or placebo 30 minutes apart, and monitored for signs/symptoms of allergic reaction throughout. The challenge is halted once pre-determined stopping criteria have been reached. DBPCFC will be performed according to the international PRACTALL consensus for best practice.¹²

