5.3.3 CONTROL GROUP

Subjects randomized to the control group will receive current standard care according to best practice (as per British Society for Allergy and Clinical Immunology guidance). This includes:

- A food allergy management plan (Figure 5), with provision of rescue medication including an adrenaline autoinjector device. Families and participants will be instructed in the prompt recognition and treatment of allergic reactions.
- **Contact information** for the team, which will include telephone contact number for the team and an email address which will be checked daily by the research team from Monday to Friday for non-urgent queries.
- **Dietary advice on peanut avoidance**. Participants will not be allowed to ingest peanut for the whole study duration (52 weeks).
- A home diary sheet, on which parents will log all accidental reactions experienced. Participants will also be
 offered an opportunity to 'opt-in' to using an electronic 'mobile app' diary in parallel to the paper-based diary.

Children (and their parents) will undergo quality-of-life assessments at 0, 3, 6 and 12 months (see 5.7.1).

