5.3.4.2 TRANSITION TO ROASTED PEANUT

After STEP 12 (approximately 4-7 months after commencement), the next updosing step involves a transition to roasted peanut. This will involve an OPEN (unblinded) abbreviated food challenge according to the following protocol:

^{*}For initial (in-hospital) updosing at the time points marked, the dose to be administered will be split into 2 doses, given 30 minutes apart: Step 6: 1 + 3 peanuts; Step 8: 1 + 1 peanut; Step 11: 1 + 3 peanuts.

Protocol 3: Open OFC to roasted PN	Roasted peanut OFC	If dose tolerated,			
TIME POINT (mins)	Peanut flour (mg) Peanut protein (mg)		continue at STEP:		
0	20	10	Do not transition to		
30	60	30	roasted PN: continue		
60	200	100	at 8 boiled PN per day		
90	600*	300*	13		
150	2000	1000	13		
180	6000 [#]	3000 [#]	16		
Cumulative dose 4440mg					
2 hours observation period following last dose to monitor for signs of reaction					

^{*}Dose to be given as 1 whole peanut (25% protein) + peanut flour to make a total dose of 300mg peanut protein

The criteria listed in Section 5.2.2 will be used to determine outcome of this food challenge.

Children who tolerate at least 300mg peanut protein (i.e. a cumulative dose of 440mg) will continue updosing at STEP 13 using roasted peanut. Those who tolerate the entire dose (4440mg) will continue at STEP 16. This is equivalent to continuing OIT at a minimum of one half roasted peanut BELOW that tolerated at this open challenge. Children who are unable to tolerate the 300mg dose will continue maintenance at 8 boiled peanuts (boiled for 30mins) until the 1 year assessment.

All subjects will also undergo repeat skin prick testing to commercial crude peanut extract, and quality-of-life assessments as described in section 5.7.1.

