5.3.4.4 PREPARATION OF BOILED AND ROASTED PEANUT FOR OIT

Families will be provided with blanched raw peanut at hospital visits, for preparation at home. Full instructions will be provided (as part of the **home diary and instruction sheet**). Peanuts (Holt Runner cultivar, supplied by the Peanut Company of Australia Ltd) will be supplied in 125g vacuum-packed batches to families on an as-needed basis, in order to monitor peanut consumption.

Families will be provided with instructions to boil the peanuts at home in batches, as follows:

- Boil 100g quantity of peanuts in a saucepan in ~600ml water for xx hours
- Drain and plunge peanuts into cold water, then drain in colander/sieve
- Lay peanuts in a single layer on a baking tray lined with baking paper
- Place tray in freezer until peanuts are 'snap frozen'
- Transfer peanuts into a plastic container and store in freezer until required.

The boiling time will be progressively reduced as depicted in Table 1 above.

In those children who tolerate roasted peanuts, families will be instructed to use commercial roasted peanuts (KP roasted peanuts) sourced from a UK supermarket. Alternatively, peanut M&Ms may be substituted for roasted peanut, where this is desired by the study participant: four roasted peanuts is equivalent to 6 peanut M&Ms.

5.4 1 YEAR ASSESSMENT

All subjects, in both the active (OIT) and control groups, will be invited to undergo a further DBPCFC to roasted PN at 12 months. Those who tolerate >1.4g of peanut protein at this challenge will be invited back for a further open challenge having stopped all peanut ingestion (including OIT doses) for 4 weeks. The challenges and outcomes are depicted in summary form in Figure 7.

[figure not shown]

Figure 7: Challenges and outcomes, months 12-13

All subjects will also undergo repeat skin prick testing to commercial crude peanut extract, and quality-of-life assessments as described in section 5.7.1.

Imperial College

5.4.1 12 MONTH DBPCFC

The DBPCFC will be performed as per Protocol 1 in Section 5.2.2. The purpose of this challenge is:

- In those who have undergone OIT, to assess for desensitisation to roasted peanut and a resulting change in threshold of clinical reactivity (Primary and Secondary outcome measures).
- In the control group, to determine the rate of natural resolution of peanut allergy and for those continuing into WP2 (where they will undergo OIT), serve as the baseline threshold of clinical reactivity to roasted peanut.

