5.8 OTHER ASSESSMENTS

5.8.1 ALLERGY SKIN PRICK TESTING

Skin prick testing (SPT) to commercial peanut extract, histamine positive and saline negative control will be performed at baseline, 6, 12, 24 months after starting OIT, and the year 3 assessments (see Fig 8), according to local standard operating procedures consistent with national guidelines.¹³ The baseline SPT will include a modified SPT to boiled peanut.

At the open food challenges (e.g. 6 month challenge), SPT will be performed by an investigator independent to the challenge so as not to influence the interpretation of challenge outcome. Additional positive controls will be included as needed to ensure blinding of the participant.

¹³ http://www.bsaci.org/Guidelines/Skin_Prick_Testing.pdf

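### Section 7.2.2 plans an active-versus-control threshold test at 6 months, but the readable text schedules no roasted-peanut challenge for controls between baseline and 12 months

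*Combined protocol and SAP*

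**What the plan says.** The analysis commitment is in Section 7.2.2: "Relative change in clinical threshold (NOAEL, LOAEL) to roasted peanut at 6 and 12 months in active vs control, using Mann-Whitney U test". Section 3.1.2 lists the same outcome at the same two times, but does not describe it as a comparison of arms.

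The text places roasted-peanut challenges in the first year as follows.

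- Baseline, everyone (Section 5.2): "All participants who fulfil eligibility criteria for the study will undergo a baseline DBPCFC to roasted peanut at enrolment".
- 12 months, everyone (Section 5.4): "All subjects, in both the active (OIT) and control groups, will be invited to undergo a further DBPCFC to roasted PN at 12 months".
- Mid-year, active arm (Section 5.3.4.2, within the active-group section 5.3.4): "After STEP 12 (approximately 4-7 months after commencement), the next updosing step involves a transition to roasted peanut". On its format: "This will involve an OPEN (unblinded) abbreviated food challenge according to the following protocol".

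For controls, Section 5.3.3 schedules this during the year: "Children (and their parents) will undergo quality-of-life assessments at 0, 3, 6 and 12 months". It lists no challenge.

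Section 5.8.1 mentions a 6-month challenge in passing, without naming an arm: "At the open food challenges (e.g. 6 month challenge), SPT will be performed by an investigator independent to the challenge".

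**The concern.** A Mann-Whitney test of change in threshold needs a baseline and a follow-up threshold in both arms. On the readable schedule, the control arm has no follow-up threshold at 6 months.

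An analyst who reaches this line has no rule to follow. The test could be dropped, the control baselines could be carried forward, or the active-arm transition result could be reported under an active-versus-control label. The last two would present an uncontrolled, open-label result, in children selected by having completed STEP 12, as though it were a randomised comparison. The trial is open label, so the choice should not be left until thresholds have been seen by arm.

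**Working it through.** **1. Challenge schedule by arm, readable text only**

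| Time | Active (30 planned) | Control (16 planned) | Source |
|---|---|---|---|
| Baseline | DBPCFC, Protocol 1 | DBPCFC, Protocol 1 | 5.2, 5.2.2 |
| Mid-year | Open challenge, Protocol 3, after STEP 12 | None listed; quality of life at 6 months | 5.3.4.2; 5.3.3 |
| 12 months | DBPCFC, Protocol 1 | DBPCFC, Protocol 1 | 5.4, 5.4.1 |

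The check with a quarter of a boiled peanut (Section 5.3.1) comes before randomisation and gives no roasted-peanut threshold.

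**2. What the test has to work with**

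The Mann-Whitney statistic is built from n(active) × n(control) pairs.

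- 6 months: at most 30 × 0 = 0 pairs. With one group empty, the statistic and its p-value are undefined.
- 12 months: at most 30 × 16 = 480 pairs. After the 20% loss assumed in Section 7.1, 30 × 0.8 = 24 active and 16 × 0.8 = 12.8, about 13, controls, so about 24 × 13 = 312 pairs. This test can be run.

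**3. When the active-arm challenge happens**

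First, the plan's own figure. Table 1 gives STEPS 1 to 11 two weeks each and STEP 12 four weeks: 11 × 2 + 4 = 26 weeks, which is the cumulative figure printed at STEP 12. The other two starting points in Section 5.3.4 give:

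- start at STEP 5: STEPS 5 to 11 are 7 × 2 = 14 weeks, plus 4 = 18 weeks;
- start at pre-A: two further steps of 2 weeks, 26 + 4 = 30 weeks.

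In months (weeks ÷ 52 × 12) these are 4.2, 6.0 and 6.9, in agreement with the 4 to 7 months stated in Section 5.3.4.2. All three are minimum times. The challenge is therefore tied to progress through updosing and has no fixed date. A child who never completes STEP 12 does not have it.

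**4. Whether it matches the baseline challenge**

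- Protocol 1 (baseline): 3, 10, 30, 100, 300, 1000, 3000 mg protein, double-blind.
- Protocol 3 (transition): 10, 30, 100, 300, 1000, 3000 mg protein, open.

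Six of the seven doses are shared. Without the 3 mg dose, Protocol 3 cannot separate a child who would react at 3 mg from one who would react at 10 mg. The larger difference is that one challenge is blinded and the other is not.

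**The case against.** The strongest objection is that part of the schedule cannot be seen. Section 5 refers the reader to Figure 2 for the main procedures; Figures 1, 2 and 7 are not reproduced in our copy, and any of them could show a visit that the text omits. This stands, and the conclusion has to be conditional on it. A reader might infer that controls definitely have no 6-month challenge; the documents available do not support that much.

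Other text could point to a control challenge.

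- The 6-month challenge in Section 5.8.1 is the most direct mention. It names no arm. It is an open challenge, in a section that times skin tests from the start of OIT, and Section 5.3.4.2 pairs the open transition challenge with skin testing. It fits the active-arm challenge and does not establish another.
- Section 3.2 says that controls undergo peanut challenges, in the plural, during the non-intervention year. No time is given. The plural may simply cover several children. The wording neither establishes nor excludes a 6-month challenge.
- Section 3 promises a 6-month assessment in all subjects, but by questionnaire. The closing line of 5.3.4.2 about all subjects concerns skin tests and quality of life.

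A reader might also take the avoidance rule in Section 5.3.3, "Participants will not be allowed to ingest peanut for the whole study duration (52 weeks", as proof that controls could not be challenged mid-year. It does not carry that weight. It is dietary advice, and the parallel rule for the active arm in 5.3.4 excepts only OIT doses, although that arm has a supervised roasted-peanut challenge in the same year.

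It is also fair to say that the two dose ladders differ by one rung, that 26 weeks is a reasonable nominal 6 months, and that Section 3.1.2 does not call for a comparison of arms. The fault may therefore be loose wording in one line of 7.2.2. That limits its weight but does not supply the missing control data.

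**Conclusion.** The point holds, subject to the figures that are not shown. On the readable text, 0 of 16 planned controls have a 6-month roasted-peanut threshold, so the 6-month between-arm test in 7.2.2 has no control data and cannot be run as written. What could be reported near 6 months is an open-label result in active-arm children who completed STEP 12, at 18 to 30 weeks or later.

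The reach is small: one timepoint of one secondary outcome. A reader might infer that the trial's efficacy evidence is compromised. It is not. The primary comparison rests on the 12-month DBPCFC in both arms, the sample size is set for that endpoint, and the 12-month threshold comparison has data in both arms. I would place it between minor and should-fix.

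The conclusion assumes that the text lists every challenge and that Figures 1, 2 and 7 add none for controls.

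**What to change.** In Section 7.2.2, restrict the active-versus-control threshold test to 12 months. Report the transition challenge on its own line as a within-active-arm, open-label result at completion of STEP 12, and give the number of randomised active children who reached it. Section 3.1.2 can stand, since it does not describe the outcome as a comparison of arms. Date the change and record the reason before thresholds are compared by arm.

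If one of the figures does schedule a 6-month challenge for controls, reconcile 5.3.3 and 7.2.2 by stating that visit in the text.

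The first route needs no new visits or data. The sponsor gives up a 6-month between-arm claim for which the readable schedule provides no control data.
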